1 BACKGROUND AND RATIONALE

1.1 Background

Peanut allergy is a common and serious condition that disproportionately affects children and is associated with severe reactions, including life-threatening anaphylaxis. Furthermore, the prevalence of peanut allergy, like other food allergies, has been rising, and is now at high levels, affecting up to 1.5% of the population (Branum et al, 2008; Sicherer and Sampson, 2014). The current standard of care in management of peanut allergy is a peanut-avoidant diet, along with education of the patient and family in the acute management of an allergic reaction, including ready access to self-injectable epinephrine. The burden of avoidance and the constant fear of accidental exposure negatively affect the health-related quality of life (QoL) for patients and their families (Primeau et al, 2000; Avery et al, 2003; Buchanan et al, 2007; Sicherer et al, 2010; Hofmann et al, 2009; Anagnostou, 2014).

In addition, peanut-avoidant diets are complicated by the difficulty of interpreting food labels and the presence of undeclared or hidden allergens in commercially prepared foods (Joshi et al, 2002; Altschul et al, 2001; Vierk et al 2002). Accidental exposures are common, with up to 50 percent of food-allergic patients having ≥ 1 allergic reaction over a 2-year period (Sicherer et al, 1998).

In early clinical trials, oral immunotherapy (OIT) for peanut allergy has demonstrated encouraging safety and efficacy results in creating a change in clinical reactivity that would protect recipients from these accidental exposures (Jones et al, 2009; Hofmann et al, 2009; Blumchen et al, 2010; Yu et al, 2012; Varshney et al, 2011; Anagnostou et al, 2014). These studies involved a period of up-dosing with increasing amounts of peanut protein, a period of maintenance therapy, and then an oral food challenge (OFC) to assess desensitization. Dosing symptoms observed in these studies have included rash, wheezing, rhinorrhea, sneezing, itching, abdominal pain, nausea, vomiting, and diarrhea. Most symptoms have been mild, consistent with a transient, low-grade allergic reaction, and have tended to diminish in frequency with increasing duration of treatment.

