3.2. SECONDARY ENDPOINTS

The secondary safety endpoints are as follows:

- Frequency of anaphylactic reaction
- Frequency of use of epinephrine as a rescue medication
- Frequency of AEs leading to withdrawal of AR101
- Frequency of AEs in each treatment regimen leading to discontinuation of extended interval dosing
- Frequency of Gastrointestinal (GI) AEIs
- Occurrence of premature discontinuation of dosing due to chronic/recurrent gastrointestinal (GI) AEs
- Frequency of accidental food allergen exposure
- In subjects with asthma, change in asthma control using the Asthma Control Test (ACT) questionnaire
- Frequency of all above safety endpoints by treatment period

The secondary efficacy endpoints are as follows:

- The proportion of subjects in each regimen tolerating a single dose of 600 mg (≥ 1043 mg cumulative) of peanut protein during their Exit DBPCFC
- The proportion of subjects in each regimen who tolerate a single dose of 300 mg (≥ 443 mg cumulative) of peanut protein during their Exit DBPCFC
- The proportion of subjects in each regimen who tolerate a single dose of 2000 mg (4043 mg cumulative) of peanut protein during their Exit DBPCFC
- Maximum tolerated dose and change from baseline* at the Maintenance DBPCFC** and each Exit DBPCFC
- Maximum severity of symptoms at each challenge dose at the Maintenance DBPCFC** and each Exit DBPCFC

Sponsor: Aimmune Therapeutics, Inc.

Protocol: ARC0004

Version: Version 1.0, 10Jul2019

- Frequency of use of epinephrine as a rescue medication at the Maintenance DBPCFC** and each Exit DBPCFC
- Change in QoL as assessed by the food allergy related quality of life questionnaire (FAQLQ) and the food allergy independent measure (FAIM) questionnaires
- Satisfaction with AR101 treatment as assessed by the TSMQ-9 questionnaire and additional questions
- Changes in peanut-specific (ps) serum immunoglobulin E (IgE) and IgG4 levels
- Changes in peanut skin prick test (SPT) wheal diameter

*Baseline is defined as the Exit DBPCFC from ARC003 for both treatment groups.

**Maintenance DBPCFC is defined only for Group 1.

Sponsor: Aimmune Therapeutics, Inc.

Protocol: ARC0004

Version: Version 1.0, 10Jul2019

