10.3. ADVERSE EVENTS

Treatment-emergent adverse events (TEAEs) will be summarized excluding symptoms recorded during the food challenges. The AE summaries will report AEs and in-clinic dosing symptoms.

If symptoms are recorded as part of an anaphylactic reaction, only the single anaphylactic reaction event will be summarized and not the individual symptoms.

All reported adverse events (AEs) will be classified into System Organ Class (SOC) and Preferred Term (PT) using Medical Dictionary for Regulatory Activities (MedDRA) version 19.1. The 5-point CoFAR severity grading scale was used for coding allergic reactions. The 3-point Muraro grading scale was used for grading the severity of anaphylactic reactions. The 5-point CTCAE severity grading scale was used for coding all other adverse events.

In Group 1, treatment-emergent adverse events are defined as those AEs with onset after the first dose of study product in ARC004 and no more than 30 days after the last dose of study product. In Group 2, as all patients are assumed to be continuing AR101 from study ARC003, all reported adverse events with onset no more than 30 days after the last dose of study product will be defined as treatment-emergent. Non treatment-emergent AEs will be included in subject listings, but not summarized. An additional summary of age group 18-55 will be included for the safety population for the overall AE summary and SAE summary.

Summaries that are displayed by system organ class and preferred terms will be ordered by descending incidence of system organ class and preferred term within each system organ class. Summaries displayed by preferred term only will be ordered by descending incidence of preferred term. Summaries of the following types will be presented:

- Overall summary of number of unique TEAEs and treatment-emergent serious adverse events (TESAEs), subject incidence of TEAEs and TESAEs meeting various criteria and exposure-adjusted incidence rates of TEAEs and TESAEs meeting various criteria, where exposure incidence rates are defined as the total number of events divided by the total number of subject-years at risk during the study period;
- Subject incidence of TEAEs by MedDRA system organ class and preferred term;
- Exposure-adjusted event rates for the most frequent TEAEs (i.e., TEAEs occurring in $\geq 5\%$ of the Safety Population) by MedDRA preferred term;

Sponsor: Aimmune Therapeutics, Inc.

Protocol: ARC0004

Version: Version 1.0, 10Jul2019

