- Subject incidence of treatment-related AEs by MedDRA system organ class, and preferred term;
- Exposure-adjusted event rates for the most frequent treatment-related AEs (i.e., treatment-related AEs occurring in $\geq 5\%$ of the Safety Population) by MedDRA preferred term;
- Subject incidence of grade ≥ 3 severity TEAEs by MedDRA system organ class and preferred term;
- Subject incidence of grade ≥ 3 severity treatment-related AEs by MedDRA system organ class and preferred term;
- Subject incidence of TESAEs by MedDRA system organ class and preferred term;
- Subject incidence of TEAEs leading to discontinuation of study product by MedDRA system organ class and preferred term;
- Subject incidence of TEAEs associated with Epinephrine use by MedDRA system organ class and preferred term.
- Subject incidence of hypersensitivity TEAEs by MedDRA system organ class and preferred term, where hypersensitivity TEAEs are all TEAEs from the in-clinic dosing CRFs and all TEAEs indicated as an allergic reaction on the AE CRF
- Subject incidence of hypersensitivity treatment-related AEs by MedDRA system organ class and preferred term;
- Exposure-adjusted event rates for the most frequent hypersensitivity TEAEs (i.e., hypersensitivity TEAEs occurring in $\geq 5\%$ of the Safety Population) by MedDRA preferred term;
- Subject incidence of TEAEs associated with nonstudy product food allergen exposure by MedDRA system organ class and preferred term; and
- Subject incidence of TEAEs leading to early withdrawal by MedDRA system organ class and preferred term

At each level of summarization (e.g., any AE, system organ class, and preferred term), subjects experiencing more than one TEAE will be counted only once within each study period. In the summary of TEAEs by severity grade, subjects will be counted once at the highest severity reported at each level of summarization.

Sponsor: Aimmune Therapeutics, Inc.

Protocol: ARC0004

Version: Version 1.0, 10Jul2019

Adverse event data will be presented in data listings by age group (4-17 years and 18-55 years), group/cohort, subject, study period, and event. Serious TEAEs; Serious DBPCFC AEs; severe, life-threatening, or fatal adverse events; anaphylactic reactions; and AEs leading to discontinuation, reduction, or interruption of the study product will be presented in separate data listings.

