10.13. EPINEPHRINE USE AS RESCUE MEDICATION

Epinephrine use is defined as any rescue medication with a preferred name of 'EPINEPHRINE' when coded as described in [Section 10.2](#).

All subjects, per protocol, are required to have epinephrine autoinjectors for use in case of a suspected anaphylactic reaction occurring outside of the clinic. There are, however, differences in how, and even if, physicians record the prescription of epinephrine autoinjectors for as-needed (PRN) use. As a consequence of this, the presence or absence of a PRN prescription for epinephrine cannot be taken to indicate epinephrine usage, regardless of whether the prescription was written prior to, or after, enrollment in the study. What is important is to be able to quantitate the number of subjects receiving doses of epinephrine and the number of doses. As epinephrine should only be administered to treat a discrete allergic reaction, each dose of epinephrine should be closely temporally associated with a specific safety event and its use recorded on the Rescue Medication CRF form. In cases where a PRN epinephrine prescription is issued after the start of study-product dosing, the sites will be queried as to if, and when, epinephrine was actually administered and to treat what specific event.

All epinephrine use will be listed for the Safety population.

In addition, epinephrine use excluding food challenges will be summarized by group/cohort and study period. The total number and percent of subjects with any episode, the number and percent of subjects with at least 1 episode, where episode refers to 1 or more doses of epinephrine within a 2-hour window, will be summarized as well as the number of episodes experienced by each subject (1, 2, 3, and > 3). For these subjects, demographics including age, age category, baseline PS IgE, and baseline PS IgE category will be included. The total number of episodes will also be presented along with the number and percent of episodes by number of doses per episode, by associated adverse

Sponsor: Aimmune Therapeutics, Inc.

Protocol: ARC0004

Version: Version 1.0, 10Jul2019

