event severity, by seriousness of associated adverse events, by relatedness of associated adverse events, and by location of episode (home/study site). For subject counts, the number of subjects at risk within each study period will be used as the denominators. For unique episode counts, the total number of episodes within each study period will be used as the denominators.

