10.14. ANAPHYLACTIC REACTIONS

All reported anaphylactic reaction events will be listed by age group, group/cohort, and subject.

Each anaphylactic reaction will be identified by the following triggers:

- DBPCFC
- Study product
- Food allergen other than study product
- Other

Anaphylactic reactions will be summarized in the Safety population separately for the following group/cohort study periods:

- Group 1: IDE and Up-Dosing, Maintenance, Overall
- Group 2 Cohort 2: QOD, BIW, and Overall
- Group 2 Cohort 1 (includes QD only)
- Group 2 Cohort 3A (includes QD only)
- Group 2 combined cohorts B and C: QD, QOD, BIW, and Overall
- Group 2 Overall QD
- Group 1, Group 2 Cohort 1, Group 2 Cohort 2, Group 2 Cohort 3A, Group 2 Cohort 3B, and Group 2 Cohort 3C by Maintenance and Exit DBPCFC

By each group/cohort and study period, the summary will include the number of anaphylactic reactions; the number of anaphylactic reactions by trigger (study product, food allergen other than study product, and other); and subject incidence of the total number of subjects experiencing an anaphylactic reaction, subjects experiencing an anaphylactic reaction by number of episodes, subjects experiencing an anaphylactic reaction by maximum severity using the Muraro grading scale ([Muraro, 2007](#); [Muraro, 2014](#)), subjects experiencing an anaphylactic reaction that was a serious adverse event, subjects experiencing an anaphylactic reaction that required epinephrine use, subjects experiencing an anaphylactic reaction by location (home or study site), and the individual symptoms involved.

Sponsor: Aimmune Therapeutics, Inc.

Protocol: ARC0004

Version: Version 1.0, 10Jul2019

If any symptom associated with an anaphylactic reaction is serious, the reaction will be classified as serious. This is in addition to, not instead of, the Muraro grade. If any symptom associated with an anaphylactic reaction is related to study product, then the reaction will be classified as related to study product.

Sponsor: Aimmune Therapeutics, Inc.

Protocol: ARC0004

Version: Version 1.0, 10Jul2019

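### SAP 10.13 and 10.14 give epinephrine use and anaphylaxis by regimen period with no subject-year rate, so columns of 4 to 56 planned weeks have no common time base and the distortion can go either way

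*SAP*

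**What the plan says.** SAP 3.2 lists anaphylactic reaction and rescue epinephrine among the secondary safety endpoints and adds "Frequency of all above safety endpoints by treatment period".

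For epinephrine, SAP 10.13 plans the number and percentage of subjects with an episode, the number of episodes per subject, and total episodes split by doses, severity, seriousness, relatedness and location. On denominators it says "For subject counts, the number of subjects at risk within each study period will be used as the denominators". Episode breakdowns are divided by the total episodes in the period, which gives shares of episodes and not a rate.

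For anaphylaxis, SAP 10.14 plans the number of reactions, also by trigger, and "subject incidence of the total number of subjects experiencing an anaphylactic reaction", with further subject counts by severity, seriousness, epinephrine use and location. Its columns include Cohort 2 (QOD, BIW, Overall), Cohort 1, Cohort 3A, combined 3B/3C (QD, QOD, BIW, Overall) and Overall QD.

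SAP 10.3 does use time at risk. In its overall summary of TEAEs and serious TEAEs, "exposure incidence rates are defined as the total number of events divided by the total number of subject-years at risk during the study period". It also plans exposure-adjusted rates for preferred terms that reach 5% of the Safety population. For epinephrine, its named summary is "Subject incidence of TEAEs associated with Epinephrine use by MedDRA system organ class and preferred term", which is incidence only.

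**The concern.** A subject percentage grows with the length of the period over which it is collected. The study is there to explore longer dosing intervals, and these tables set regimen periods of quite different length beside each other. Even in a purely descriptive report, a lower percentage over a shorter period can be read as a safer regimen, and a higher one over a longer period as a riskier regimen, when the risk per unit time is the same. Protocol section 9 leaves the handling of varying exposure times to the SAP. The SAP handles it for TEAEs in 10.3 but not in the two sections devoted to these endpoints.

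**Working it through.** **The plan's own figure.** The one probability that ARC004 states for itself is an 80% chance of seeing at least one AE with about 400 subjects and a background rate of 4 per 1,000. It reproduces: 1 - 0.996^400 = 0.799. The present point does not depend on it.

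**Inputs from the documents.**
- Planned lengths (SAP 2.3): QOD 4 weeks; BIW 24 weeks; QD 28 weeks in Cohorts 1, 3B and 3C; QD 56 weeks in Cohort 3A.
- Planned sizes (Protocol 7.8.3): Cohort 1, 120; Cohort 2, 50; Cohort 3, 175 in equal thirds (58.3 each).
- SAP 2.3 also records that 3C subjects on BIW were to stay on BIW, with no end date and no number of subjects. If held to week 84, their BIW time is 24 + 28 = 52 weeks.

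**Assumptions.** One constant rate h per subject-year, equal in every regimen, and no dropout. The documents give no event rate, so h runs from 0.02 to 1.0.

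**Formulas.**
- Expected subject percentage over w weeks: I(w) = 1 - exp(-h × w / 52.18).
- Pooled Group 2 QD: (120 × I(28) + 58.3 × I(56) + 116.7 × I(28)) / 295.
- Pooled 3B/3C BIW with all of 3C held to week 84: (I(24) + I(52)) / 2.

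| Column | h = 0.02 | h = 0.2 | h = 1.0 |
|---|---|---|---|
| QOD, 4 weeks | 0.15% | 1.52% | 7.38% |
| BIW, 24 weeks | 0.92% | 8.79% | 36.87% |
| QD, 28 weeks | 1.07% | 10.18% | 41.53% |
| QD, 56 weeks (3A) | 2.12% | 19.32% | 65.81% |
| Pooled Group 2 QD | 1.28% | 11.98% | 46.33% |
| 3B/3C BIW, 3C held to week 84 | 1.44% | 13.43% | 49.98% |

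**Ratios on planned lengths (equal risk, so the fair value is 1).**
- QOD against 28-week QD: 0.144, 0.150, 0.178.
- 24-week BIW against 3A: 0.431, 0.455, 0.560.
- 24-week BIW against pooled Group 2 QD: 0.717, 0.733, 0.796.
- 24-week BIW against 28-week QD: 0.858, 0.864, 0.888.
- Cohort 2 Overall (4 + 24 = 28 weeks) against Cohort 1 QD (28 weeks): 1.00.

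**Ratios for pooled 3B/3C BIW with all of 3C held to week 84.**
- Against any 28-week QD column (its own QD period or Cohort 1): 1.353, 1.320, 1.203.
- Against pooled Group 2 QD: 1.132, 1.121, 1.079.
- Against 3A: 1.44/2.12 = 0.68, 13.43/19.32 = 0.70, 49.98/65.81 = 0.76.

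The crossing points follow from mean length when h is small. Pooled 3B/3C BIW matches 28 weeks when (24 + x)/2 = 28, so x = 32 weeks of BIW in 3C. It matches the pooled QD mean of 33.5 weeks when x is about 43.

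**What a rate would show.** Under equal risk, events per subject-year have the same expectation in every column. Subject-years at planned sizes are 50 × 4/52.18 = 3.8 for Cohort 2 QOD, 50 × 24/52.18 = 23.0 for Cohort 2 BIW, and 120 × 28/52.18 = 64.4 for Cohort 1 QD. At h = 0.2 the expected episodes are 0.8, 4.6 and 12.9.

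**The case against.** **SAP 10.3 already covers this.** It does so in part. An anaphylactic reaction enters the 10.3 tables as one event ("only the single anaphylactic reaction event will be summarized and not the individual symptoms"), so the term gets an exposure-adjusted rate if it reaches 5% of the Safety population. Under a constant rate at planned sizes, that happens at about 0.04-0.05 per subject-year, and at a lower rate if Group 1 up-dosing carries more risk. Either endpoint might also be among the criteria that the overall summary mentions but does not list, and the table shells are a separate document that cannot be checked here. It would therefore be wrong to infer that the SAP ignores exposure time or that anaphylaxis will certainly have no rate. What remains is that no rate of epinephrine episodes is named anywhere, and any anaphylaxis rate would not be tied to the trigger or severity detail of 10.14.

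**Length-matched columns exist.** True. Cohort 2 Overall and Cohort 1 QD both cover 28 planned weeks, and 24-week BIW against 28-week QD is only 11-14% low, too little to see at 4.4 expected affected subjects in Cohort 2 BIW (h = 0.2). The large ratios come from the 4-week QOD lead-in and from 56-week 3A.

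**The columns a reader sees together.** SAP section 10 puts Cohort 2 in Part 1 of the event tables and Cohorts 1, 3A, 3B/3C and Overall QD in Part 2. The BIW column beside the Group 2 QD columns is therefore pooled 3B/3C, whose direction is unknown because 3C was held on BIW. This stands, and it rules out a one-directional claim.

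**The tables are descriptive, and exposure is tabulated.** SAP 6.4 plans no formal comparison. Because SAP 10.1 gives exposure duration by period, a reader could approximate a Group 2 rate by hand. Both are true, and they limit the harm to a possible misreading. No planned estimate is wrong.

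**Conclusion.** The gap is real and modest. SAP 10.13 and 10.14 plan counts and percentages over periods of unequal length, with no common time base.

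- On planned lengths, equal risk would display as 0.14-0.18 (QOD against 28-week QD), 0.43-0.56 (24-week BIW against 3A), 0.72-0.80 (against pooled Group 2 QD) and 0.86-0.89 (against 28-week QD).
- With all of 3C on BIW to week 84, the pooled 3B/3C BIW column would instead display 1.20-1.35 of a 28-week QD column and 1.08-1.13 of pooled Group 2 QD, while staying below 3A at 0.68-0.76.

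These figures assume a constant, equal rate of 0.02-1.0 per subject-year and no dropout. At the low end the counts are too small to read (about 0.5 affected subjects in Cohort 2 BIW and 1.2 in 3A). The practical gap is mainly epinephrine.

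Two stronger readings are tempting. One is that the tables systematically make nondaily dosing look safer; the 3C decision in SAP 2.3 means that the sign depends on the column. The other is that subject-year rates would make the regimens comparable. They would not if risk is per dose: equal risk per dose gives a BIW/QD subject-year ratio of 2/7 = 0.29. Nor would they if risk falls with time, and Protocol 1.1 says that dosing symptoms "have tended to diminish in frequency with increasing duration of treatment", while QD comes first in 3B and 3C.

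**What to change.** In SAP 10.13, and in 10.14 for consistency, add two rows to each group/cohort dosing-period column: subject-years at risk, and episodes (or reactions) per subject-year by the 10.3 definition. The food-challenge columns in 10.14 can stay as they are.

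Add a footnote that these rates do not by themselves make regimens comparable if risk is per dose or falls with time on treatment.

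If an interval is shown, an exact Poisson interval is enough, labelled descriptive and as ignoring repeat episodes within a subject. More elaborate variance models would not suit an SAP that plans no modelling (6.2), with about five expected episodes in a column.

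The cost is SAP wording and a few table rows, with no new data. Group 2 period dates are already in the SAP 10.1 table. Group 1 extended maintenance is defined in SAP 7.5 but has no row in that table, so its first and last dose dates must be added. The downside is imprecise rates in short periods. For example, 5 episodes in the 23.0 subject-years of Cohort 2 BIW give 5/23.0 = 0.22 per subject-year, with exact Poisson limits 1.62/23.0 = 0.07 and 11.67/23.0 = 0.51. Showing that width is more informative than a bare percentage.

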10.14. ANAPHYLACTIC REACTIONS

All reported anaphylactic reaction events will be listed by age group, group/cohort, and subject.

Each anaphylactic reaction will be identified by the following triggers:

- DBPCFC
- Study product
- Food allergen other than study product
- Other

Anaphylactic reactions will be summarized in the Safety population separately for the following group/cohort study periods:

- Group 1: IDE and Up-Dosing, Maintenance, Overall
- Group 2 Cohort 2: QOD, BIW, and Overall
- Group 2 Cohort 1 (includes QD only)
- Group 2 Cohort 3A (includes QD only)
- Group 2 combined cohorts B and C: QD, QOD, BIW, and Overall
- Group 2 Overall QD
- Group 1, Group 2 Cohort 1, Group 2 Cohort 2, Group 2 Cohort 3A, Group 2 Cohort 3B, and Group 2 Cohort 3C by Maintenance and Exit DBPCFC

By each group/cohort and study period, the summary will include the number of anaphylactic reactions; the number of anaphylactic reactions by trigger (study product, food allergen other than study product, and other); and subject incidence of the total number of subjects experiencing an anaphylactic reaction, subjects experiencing an anaphylactic reaction by number of episodes, subjects experiencing an anaphylactic reaction by maximum severity using the Muraro grading scale ([Muraro, 2007](#); [Muraro, 2014](#)), subjects experiencing an anaphylactic reaction that was a serious adverse event, subjects experiencing an anaphylactic reaction that required epinephrine use, subjects experiencing an anaphylactic reaction by location (home or study site), and the individual symptoms involved.

Sponsor: Aimmune Therapeutics, Inc.

Protocol: ARC0004

Version: Version 1.0, 10Jul2019

If any symptom associated with an anaphylactic reaction is serious, the reaction will be classified as serious. This is in addition to, not instead of, the Muraro grade. If any symptom associated with an anaphylactic reaction is related to study product, then the reaction will be classified as related to study product.

Sponsor: Aimmune Therapeutics, Inc.

Protocol: ARC0004

Version: Version 1.0, 10Jul2019

